3.1 Data analysis and dissemination of results (publications and conference materials)

## 6.2. Data Collection Tool

Two digital questionnaires (to be completed directly within the App) will be used: one at time T0 (baseline) and the second at time T1 (three months) and T2 (six months). In particular:

1. Within the questionnaire administered at baseline, the validated Multidimensional Health Locus of Control (MHLC) questionnaire is included. It contains eighteen questions through which the Locus of Control of the participants will be assessed.
2. Informed choice will be evaluated through three items: knowledge (score of at least 7 out of 13), attitude (score > 24), and intention (actual behaviour). Among these, the first two items must necessarily be satisfied in order to define that the subject is informed about the choice.
3. The level of knowledge related to healthy behaviours and primary prevention will be assessed through the 13 questions on primary prevention and healthy lifestyle behaviours. Based on the number of correct answers, subjects will be classified into three categories: low knowledge (0 to 5 out of 13), good knowledge (6 to 8 out of 13), and excellent knowledge (9 to 13 out of 13).
4. Decision conflict, customer satisfaction, and the acceptability of the App will be assessed at T1 and T2 through specific items of the second questionnaire (decision-making process, satisfaction, and decision-aid acceptability).

In addition, Brescia LHA will provide data on residents born in 1973 and 1974, by sex, and the number of subjects, by sex, who actually completed the FOBT screening.

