## **3. Endpoint**

### **3.1. Primary Endpoint**

The primary endpoint is users' awareness in the field of cancer prevention, specifically regarding colorectal cancer screening. This will be assessed as a dichotomous variable by combining measures of knowledge, attitudes, and intentions, according to the three-dimensional framework by Marteau et al. and comparing results between the two study arms. A participant will be considered to have made an informed choice if they have adequate knowledge and if their attitudes and behaviors are consistent. Among these three dimensions, adequate knowledge and consistent attitudes must be satisfied for the choice to be classified as "informed".

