### **3.2. Secondary Endpoint**

1. Screening adherence rate, calculated as the ratio between the number of individuals who completed the screening and the total number of individuals invited to participate in the screening program in the two study arms.
2. Level of knowledge related to healthy behaviors and primary prevention in the two study arms will be measured using a digital questionnaire containing 13 questions on primary prevention and healthy lifestyle behaviors.
3. Decision conflict, customer satisfaction, and the acceptability of the application will be assessed through additional questions included in the same digital questionnaire.

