1. Brescia LHA will be responsible for promoting the research among subjects who may be eligible for recruitment. Brescia LHA will send invitation letters to the cohort of users born in 1973 and 1974, who will receive their first invitation to undergo the faecal occult blood test screening, residing in the Brescia LHA area. In the letter, citizens will be invited to download a smartphone application, through which they will provide their consent to the use of their data by the University of Pavia.  
Brescia LHA will provide the University of Pavia with informational material containing notions on primary prevention and healthy lifestyles, as well as data on the number of residents born in 1973 and 1974 by sex and the number of individuals, by sex, who will have completed the screening by the end of the year.
2. The Department of Public Health, Experimental and Forensic Medicine of the University of Pavia will be responsible for:
  - Defining the research project operationally;
  - Collecting data and consent from participants;
  - Developing a communication and information tool aimed at the population in order to achieve the objectives of the regional programs PP02 and PL14.

The evaluation of the research results will be returned to Brescia LHA in anonymous form.

The data flow diagram is shown below.

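### Section 6.2 scores informed choice by a mandatory one-sided attitude cut and gives intention no criterion, whereas section 3.1 requires attitude and behaviour to agree

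*Combined protocol and SAP*

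**What the plan says.** All references are to the combined protocol and SAP.

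- **Section 3.1** describes a yes/no endpoint formed "by combining measures of knowledge, attitudes, and intentions". The rule follows: "A participant will be considered to have made an informed choice if they have adequate knowledge and if their attitudes and behaviors are consistent". The section closes: "Among these three dimensions, adequate knowledge and consistent attitudes must be satisfied for the choice to be classified as" informed.
- **Section 6.2, item 2** gives the operational criteria: "knowledge (score of at least 7 out of 13), attitude (score > 24), and intention (actual behaviour"). It continues: "Among these, the first two items must necessarily be satisfied". Knowledge and attitude each have a cut-off. The third item has no cut-off, no coding and no stated relation to attitude.
- **Section 7** has intention asked of every participant at T0, T1 and T2.
- **Screening completion** is described in section 6.2 as a figure supplied by the local health authority, "the number of subjects, by sex, who actually completed the FOBT screening", and in section 10 as "the number of individuals, by sex, who will have completed the screening by the end of the year".
- **Section 8.2** compares the two proportions by a chi-square test. It adds no combining rule and names no time point for the comparison.

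**The concern.** Consistency is a relation between two measurements, so it can be met at either end of an attitude scale. A score above 24 is a condition on one measurement and can be met on one side only. Section 6.2 puts the second in place of the first.

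This is the primary endpoint. Two analysts who follow 3.1 and 6.2 respectively could report different results from the same data. Section 1 says that a decision either to have or not to have screening should be informed, yet under 6.2 only people above the attitude cut can qualify. If the app shifts attitude and leaves knowledge and consistency unchanged, 6.2 would register a gain in informed choice where 3.1 would register none.

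**Working it through.** **1. The two rules side by side.** Take participants with knowledge of at least 7/13, and suppose that 24 separates opposing attitudes.

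| Attitude | Intention or behaviour matches attitude | 3.1 | 6.2, two items sufficient | 6.2, two items only necessary |
|---|---|---|---|---|
| > 24 | yes | informed | informed | undefined |
| > 24 | no | not informed | informed | undefined |
| ≤ 24 | yes | informed | not informed | not informed |
| ≤ 24 | no | not informed | not informed | not informed |

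The third row conflicts with 3.1 on both readings of 6.2. The second row conflicts if two items suffice. If they are only necessary, everyone above the cut waits on a criterion that is not given.

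**2. The plan's own sample size.** Inputs from section 8.1: 50% informed, 10-point difference, 90% power, two-sided 5%. With pooled variance under the null:

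n = [1.960·√(2·0.55·0.45) + 1.282·√(0.50·0.50 + 0.60·0.40)]² / 0.10² = 518.04, so 519 per group, as stated. Then 1,038 / 0.5 × 1.2 = 2,491.2, so 2,492, also as stated. Neither figure depends on which definition applies.

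**3. Illustration of the arm difference.** None of these rates is in the documents. Let k be the share with adequate knowledge, a the share with attitude above 24, and c the share whose intention or behaviour matches their attitude, the same on both sides of the cut. Assume that knowledge is independent of attitude and consistency, and that 24 is a valid dividing point. Set k = 0.60 and c = 0.90 in both arms.

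- 3.1: k·[a·c + (1−a)·c] = k·c = 0.540 in both arms, whatever a is. Difference 0.0.
- 6.2, two items sufficient: k·a.
- 6.2, with consistency also required: k·a·c.

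| Attitude > 24, control vs app | k·a | Difference | k·a·c | Difference |
|---|---|---|---|---|
| 80% vs 90% | 0.480 vs 0.540 | +6.0 points | 0.432 vs 0.486 | +5.4 points |
| 80% vs 85% | 0.480 vs 0.510 | +3.0 points | 0.432 vs 0.459 | +2.7 points |

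**4. How often the chi-square test would be significant at 519 per group.** Probability ≈ Φ[(d − 1.96·s₀)/s₁], where d is the difference, s₀ = √(2·p̄(1−p̄)/n) and s₁ = √((p₁(1−p₁) + p₂(1−p₂))/n). The opposite tail adds almost nothing.

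- 0.480 vs 0.540: (0.060 − 0.0608)/0.0310, about 49%.
- 0.432 vs 0.486: (0.054 − 0.0606)/0.0309, about 42%.
- 0.480 vs 0.510: about 16%.
- 0.432 vs 0.459: about 14%.
- 3.1 rule, 0.540 vs 0.540: 5%, the nominal level.

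**The case against.** **The closing sentence of 3.1 resembles 6.2.** It too says that two of three dimensions must be met, so 6.2 can be read as a clumsy version of it. But the sentence asks for attitudes that are consistent, not for a score above a cut, and does not say with what they must be consistent. This shows that 3.1 is itself loose; it does not supply a rule.

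**Perhaps only people who screened are analysed.** Section 8.1 divides the sample size by 50% adherence. If the 519 per group were all screeners, behaviour would be constant and, with a high score meaning favourable, attitude above 24 would itself be the consistency check. Section 8.2 states no such restriction, so this reading cannot be relied on.

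**The scale is not shown.** The questionnaires, cited as Annexes 4 and 5 in section 6.1, are not in the text available. This stands as a limit on the size of the problem: if nobody at or below 24 holds an opposing attitude, the third row of the table is empty. It does not supply the missing criterion for the third item or remove the mandatory cut.

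**The illustration is constructed.** This stands. No document supports a 10-point attitude shift with knowledge unchanged. The percentages also depend on group size: with recruitment to 2,500 and 20% drop-out there would be 2,500 × 0.8 / 2 = 1,000 per arm, and the 10-point case would give about 77% or 68%.

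**A reader might infer that the documents contradict each other on behaviour data, or that behaviour is unobtainable.** They support neither. The authority's counts by sex are cohort figures supplied in addition to the questionnaires, while section 3.2 defines adherence over "the total number of individuals invited to participate in the screening program in the two study arms". These can coexist, and self-report in the app is not excluded. What can be said is that no per-participant source of behaviour is described.

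**Conclusion.** Wrong as written. Section 6.2 does not implement the consistency that section 3.1 requires, leaves the third item without a criterion, and no other section gives a combining rule. That conclusion rests on the text alone.

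The consequence is that the primary comparison can move with attitude level alone. Under the assumed rates above, the spurious difference is +6.0 or +5.4 points for a 10-point attitude shift and +3.0 or +2.7 for a 5-point shift, against 0.0 under consistency. These are not estimates for this trial; the size and direction here are unknown.

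Two stronger readings are tempting. One is that the trial is biased in favour of the app, with a false-positive rate of 42% to 49%. The documents give no attitude distribution in either arm, so this cannot be claimed. The other is that informed refusal specifically is excluded. That holds only if a high score means a favourable attitude, which the available text does not show.

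**What to change.** State one algorithm, in the same words, in sections 3.1 and 6.2: informed choice means knowledge of at least 7/13 and attitude concordant, in either direction, with one named individual-level measure at one stated time point. Say that these conditions are jointly necessary and sufficient, and rewrite the closing sentence of 3.1 to match.

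- **Measure.** The simplest is the questionnaire intention item already collected at T1 and T2. Self-reported or linked test completion is possible only if it is obtained per participant, which the documents do not describe.
- **Scoring.** State the attitude scale's range and direction, whether 24 is its dividing point, how neutral scores are handled, and how intention is dichotomised.
- **Timing.** Date the rule before arm-level outcomes are seen. Enrolment was planned for January 2023 to August 2024, so outcomes may already exist. If they have been seen, report both rules and label the change.

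**Cost.** With intention, the work is rewording and recoding of items already held, provided the item can be dichotomised. With test completion, it also needs per-participant collection or linkage. Either way this is a documented change to the primary endpoint definition, and the 50% and 10-point planning assumptions must be reconfirmed for it. If they hold, 519 per group stands. By the same formula any 10-point difference needs at most 524 per group (45% vs 55%: 523.3).

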## 7. Study Duration and Planned Assessments

The duration of the study will be 30 months. The enrollment period will take place from January 2023 to August 2024, in conjunction with the invitation sent by Brescia LHA to citizens born in 1973 and 1974 to undergo FOBT screening. Following the completion of the informed consent and the baseline questionnaire, users will be progressively randomized.

The total enrolment period will last 20 months. Assessments for each subject will be performed at baseline (T0), at 3 months (T1), and at 6 months (T2).

**T0:** questionnaire collecting information on socio-demographic data, risk perception, knowledge, attitude, intention, and Locus of Control.

**T1:** questionnaire collecting information on risk perception, knowledge, attitude, intention, decision-making process, customer satisfaction, and application acceptability.

**T2:** same questionnaire administered at T1.

## 8. Statistical Aspects

### 8.1. Sample size

Based on previous studies, we considered an absolute difference of 10% between the proportion of individuals who make an informed choice and those who do not to be the minimum important difference for the sample size calculation. Assuming that the proportion of individuals making an informed choice is 50%, with a power of 90% and a two-sided significance level of 5%, 519 subjects per group are required, for a total of 1,038 subjects.

Considering an estimated colorectal cancer screening adherence rate of 50% in the province of Brescia and a probable drop-out rate of 20%, at least 2,492 subjects will need to participate in the study.

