### 6.1. Intervention Procedures

All subjects who meet the inclusion criteria will receive, through an attachment to the invitation letter (Annex 1) for screening, the instructions on how to download the application on their smartphone. Once downloaded, the application will allow exclusively to complete the informed consent (Annex 2), to read the privacy policy (Annex 3) and subsequently the baseline questionnaire (T0) (Annex 4), in digital format. Afterwards, the users will be progressively randomized into an intervention arm and a control arm. Recruitment will be stopped upon enrollment of subject number 2500.

Subjects assigned to the control arm will have access to the mobile application in a limited version. In a specific section, there will be standardized and digitalized scientific dissemination documents aimed at providing information on primary prevention, healthy and correct lifestyles, and on colorectal cancer screening.

Subjects assigned to the intervention arm will have access to the full version of the application. In particular, in addition to the specific section available for the control group, users will be presented with the aforementioned information in the form of daily “pills.” Moreover, by completing one quiz per week and one twice a week, the user will be able to earn points based on the number of correct answers provided. The quizzes will be of two types: the first, weekly, will consist of 10 questions, 5 regarding primary prevention topics and 5 on general knowledge; the second, every 3 days, will consist of 3 prevention-related questions. Users will have 15 seconds to answer each question, and the score, in case of a correct answer, will be assigned based on the time taken to select it.

For both arms, it will be possible to fill in a follow-up questionnaire at T1 and T2 (Annex 5), respectively at 3 and 6 months from enrollment.

The project foresees a total duration of 30 months.

It is possible to identify three main phases:

**Phase 1**, called **Project Start-Up**, consists of:

- 1.1 Drafting of the Study Protocol
- 1.2 Design of the CRF, creation of the electronic database and related completion manual
- 1.3 Definition of the Statistical Analysis Plan (SAP)
- 1.4 Preparation and submission of the documentation to the relevant Ethics Committee

**Phase 2**, called **Study Set-Up**, includes:

- 2.1 Identification of the cohort, patient enrollment and randomization

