## **8.2. Statistical Methods**

Descriptive statistics will be used to describe the collected variables: mean and standard deviation, median and interquartile range for quantitative variables, and absolute frequencies and percentages for qualitative variables. The comparison between the proportion of subjects making an informed choice in the two groups will be evaluated using the Chi-square test, as will the comparison between the proportion of subjects adhering to screening in the two arms.

Median scores obtained from the knowledge questionnaire will be evaluated using the Friedman test at the three time points.

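### The 2,492 in section 8.1 rests on an unexplained 50% adherence factor and matches drop-out applied as ×1.2; by division the requirement is 2,595 with the factor or 1,298 without it

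*Combined protocol and SAP*

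**What the plan says.** Section 8.1 (Sample size) takes 50% informed choice, an absolute difference of 10 percentage points, 90% power and a two-sided 5% level, and concludes that "519 subjects per group are required, for a total of 1,038 subjects". It then brings in "an estimated colorectal cancer screening adherence rate of 50% in the province of Brescia". Together with an allowance for loss to follow-up, this leads to the final figure: "a probable drop-out rate of 20%, at least 2,492 subjects will need to participate in the study". It shows no formula for this second step.

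Other sections that bear on it:

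- Section 6.1 (Intervention Procedures) places randomisation after consent and the baseline questionnaire. It adds: "Recruitment will be stopped upon enrollment of subject number 2500".
- Section 6.1 also says: "For both arms, it will be possible to fill in a follow-up questionnaire at T1 and T2". Section 7 plans the baseline, 3-month and 6-month assessments for every subject.
- Section 8.2 (Statistical Methods) says: "The comparison between the proportion of subjects making an informed choice in the two groups will be evaluated using the Chi-square test". It does not limit this to people who were screened.
- Sections 3.1 and 6.2 build informed choice from knowledge, attitude and intention or behaviour. Knowledge and attitude are the two parts that must be met.
- Section 3.2 makes screening adherence a separate secondary endpoint, with "the total number of individuals invited to participate in the screening program in the two study arms" as its denominator.

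**The concern.** The step from 1,038 to 2,492 raises two questions.

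**Why the 50% factor is there.** Dividing by 0.5 is justified only if half of those enrolled will not contribute to the primary comparison. Section 8.1 labels the 50% as an estimate for the province, but gives no source and no reason for applying it to people already enrolled and randomised. A participant who does not take the test can still complete the questionnaires, and not being screened is itself a behaviour to set against attitude.

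**How drop-out was applied.** The figure matches multiplication by 1.2, which does not replace a 20% loss.

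The evaluable target is clear, but the share of enrolled participants expected to be evaluable is not. The stated total implies 1,038/2,492 = 41.7%, the plan's two factors imply 0.5 × 0.8 = 40%, and drop-out alone implies 80%. The required enrolment therefore differs about twofold depending on a factor that the plan does not explain. Its reading also affects who is analysed: leaving out unscreened participants would select on a post-randomisation outcome that the trial itself compares between arms.

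**Working it through.** **Inputs (section 8.1 unless noted).** Proportions 0.50 and 0.60; two-sided α = 0.05 (z = 1.960); power 90% (z = 1.2816); adherence 50%; drop-out 20%; recruitment stop 2,500 (section 6.1). Equal allocation is inferred from the equal group sizes.

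**1. Evaluable number.** Pooled two-proportion formula without continuity correction, with mean proportion 0.55:

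n = [1.960 × √(2 × 0.55 × 0.45) + 1.2816 × √(0.5 × 0.5 + 0.6 × 0.4)]² / 0.10² = 518.04, so 519 per arm and 1,038 in total. This reproduces the plan.

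**2. The stated total.** Combinations of the two factors:

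| Calculation | Result |
|---|---|
| 1,038 / 0.5 × 1.2 | 2,491.2, rounded up to **2,492** |
| 1,038 / 0.5 / 0.8 | 2,595 |
| 1,038 × 1.2 | 1,245.6 |
| 1,038 / 0.8 | 1,297.5, rounded up to 1,298 |
| 1,038 / (1 − 0.5 − 0.2) | 3,460 |

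Only the first matches. Rounding by arm agrees: 519 / 0.5 × 1.2 = 1,245.6, so 1,246 × 2 = 2,492.

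**3. What ×1.2 covers.** With the adherence factor, 2,492 × 0.5 = 1,246. The loss that leaves 1,038 is 1 − 1,038/1,246 = 16.7%, not 20%. At 20% drop-out, 2,492 × 0.5 × 0.8 = 996.8 evaluable.

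**4. Requirement and power with drop-out by division.** Power = Φ{[0.10 × √n − 1.960 × √(2 × 0.55 × 0.45)] / √(0.5 × 0.5 + 0.6 × 0.4)}, where n is the evaluable number per arm.

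| | Required total | Enrolled | Evaluable | Per arm | Power |
|---|---|---|---|---|---|
| Factor kept | 2,595 | 2,492 | 996.8 | 498.4 | 88.9% |
| Factor kept | 2,595 | 2,500 | 1,000 | 500 | 89.0% |
| Factor dropped | 1,298 | 2,500 | 2,000 | 1,000 | 99.5% |

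With the factor kept, the stop is 2,595 − 2,500 = 95 below the requirement. With it dropped, the stop is 2,500 − 1,298 = 1,202 above.

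**5. Sensitivity to drop-out (10% and 30% are assumptions, not plan figures).**

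| Drop-out | Kept: required | Kept: power at 2,500 | Dropped: required | Dropped: power at 2,500 |
|---|---|---|---|---|
| 10% | 2,307 | 92.2% | 1,154 | 99.8% |
| 20% | 2,595 | 89.0% | 1,298 | 99.5% |
| 30% | 2,966 | 84.6% | 1,483 | 98.8% |

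**The case against.** The strongest objection is that little follows from this. The drop-out slip costs about one point of power if the factor is meant, and nothing if it is not. No test changes and no participants are added. That stands, and it is why the point is minor.

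The ×1.2 route is also a reconstruction, since the plan shows no formula. The exact match is strong evidence of the arithmetic but not of the authors' intent. The case does not depend on it: whatever route was used, 2,492 is not what the plan's own two factors require.

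The factor might have been meant to convert invitations into participants. The text does not allow this: 2,492 is a number who take part, and the stop at 2,500 counts enrolled subjects. It might have been meant to support the adherence endpoint, but section 8.1 sizes the trial on informed choice alone and gives no power calculation for adherence.

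Two cautions are fair. The denominator in section 3.2 concerns the secondary endpoint and invited people, so it is only supporting evidence; sections 6.1, 7 and 8.2 carry the argument. And section 6.2 describes the health authority's screening data as counts by sex, so how behaviour is obtained for each person is unclear. That is a separate gap, and it gives no reason for halving the evaluable sample.

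Finally, if each arm is rounded up separately the requirement is 2,596 rather than 2,595, which changes nothing.

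**Conclusion.** The concern holds, as a minor point. The 1,038 is correct. The 2,492 is not a valid requirement on either reading: with the adherence factor it is 103 too low (2,595 − 2,492), and without it the figure is about twice what the target needs (2,492/1,298 = 1.92). At the 2,500 stop, power is about 89% or about 99.5%, against the stated 90%.

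These figures rest on the plan's own 50% versus 60%, equal arms and 20% drop-out. The 99.5% applies to the 80% of participants with data; if all 2,500 were analysed (1,250 per arm) it would be 99.9%. The conclusion that the factor is unexplained rests on the plan's text, not on any view of what adherence in the province will be.

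**What to change.** Keep the 2,500 stop. In section 8.1, show the formula, apply drop-out as division by 0.8, and adopt one of two statements:

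- **(a) Keep the factor.** Explain why half of the participants would not contribute to the primary endpoint. Restate the requirement as 2,595, acknowledge that the stop in section 6.1 is 95 below it, and give the power at 2,500 as about 89%.
- **(b) Remove the factor.** State in section 8.2 that the primary analysis includes all randomised participants with primary-endpoint data, whether or not they were screened. Restate the requirement as 1,298 and the power at 2,500 as about 99.5% (1,000 evaluable per arm at 20% drop-out).

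The cost is wording in section 8.1, plus one sentence in section 8.2 under (b). Neither option needs extra participants.
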